11.3.8. Lacrimal Function

Lacrimal Function

The lacrimal function will be assessed using Schirmer's test. The Schirmer's test is to be performed at Baseline/Screening and Visit 2. At each time point, i) the amount of wetting of strip measured in millimetre scale, in 5 minutes ii) the time taken to complete saturation of the strip.

The ratio of strip wetted to time (i/ii) will give mm of paper wetter per minute.

Strip wet per minute = (mm of paper wet/time in seconds) x 60

The time will be given in minute seconds format and will be transformed to seconds.

This value will be summarised and to correlate with imaging parameters. If one of the values (i or ii) is missing at one timepoint then the same value from the other time point will be used to calculate the ratio for a specific eye. If the measure of the rate is missing at both time points, then ratio will be set to missing.

11.4. Appendix 4: Premature Withdrawals & Handling of Missing Data

11.4.1. Premature Withdrawals

Element	Reporting Detail
General	
 • Subject study completion (i.e. as specified in the protocol) was defined as one who completed all phases of the study including the follow up. • Withdrawn subjects may be replaced in the study at the discretion of the sponsor. • All available data from subjects who were withdrawn from the study will be listed and all available planned data will be included in summary tables and figures, unless otherwise specified.

11.4.2. Handling of Missing Data

Element	Reporting Detail
General	
 • Missing data occurs when any requested data is not provided, leading to blank fields on the collection instrument: 
 ○ These data will be indicated by the use of a “blank” in subject listing displays. Unless all data for a specific visit are missing in which case the data is excluded from the table. ○ Answers such as “Not applicable” and “Not evaluable” are not considered to be missing data and should be displayed as such.
Outliers	
 • Any subjects excluded from the summaries and/or statistical analyses will be documented along with the reason for exclusion in the clinical study report.

11.4.2.1. Handling of Missing Dates

Completely missing start or end dates will remain missing, with no imputation applied.

11.4.2.2. Handling of Partial Dates

Element	Reporting Detail
Concomitant Medications	
 ○ Partial dates for any concomitant medications recorded in the CRF will be imputed using the following convention: ○ If the partial date is a start date, a '01' will be used for the day and 'Jan' will be used for the month ○ If the partial date is a stop date, a '28/29/30/31' will be used for the day (dependent on the month and year) and 'Dec' will be used for the month. Unless this is after the end date of study; in this case the end of study date will be used. ○ The recorded partial date will be displayed in listings.
Adverse Events	
 ○ Any partial dates for adverse events will be raised to data management. If the full date cannot be ascertained, the following assumptions will be made:

Element	Reporting Detail
	
 ○ If the partial date is a start date, a '01' will be used for the day and 'Jan' will be used for the month. ○ However, if these results in a date prior to Visit 1 and the event could possibly have occurred during study from the partial information, then the Visit 1 date will be assumed to be the start date. ○ The AE will then be considered to start on-study (worse case). ○ If the partial date is a stop date, a '28/29/30/31' will be used for the day (dependent on the month and year) and 'Dec' will be used for the month. Unless this is after the end date of study; in this case the end of study date will be used. ○ The recorded partial date will be displayed in listings.

11.4.2.3. Handling of Missing Data for Statistical Analysis

Missing data will remain missing with no imputation applied for the purposes of statistical analysis.

11.5. Appendix 5: Values of Potential Clinical Importance

11.5.1. Vital Signs

Vital Sign Parameter (Absolute)	Units	Clinical Concern Range	
		Lower	Upper
Systolic Blood Pressure	mmHg	< 85	> 160
Diastolic Blood Pressure	mmHg	< 45	> 100
Heart Rate	bpm	< 40	> 110

11.5.2. Laboratory Values

Haematology				
Laboratory Parameter	Units	Category	Clinical Concern Range	
			Low Flag (< x)	High Flag (>x)
Hematocrit	Ratio of 1	Male		0.54
		Female		0.54
		Δ from BL	↓0.075	
Hemoglobin	g/L	Male		180
		Female		180
		Δ from BL	↓25	
Lymphocytes	x10 ⁹ /L		0.8	
Neutrophil Count	x10 ⁹ /L		1.5	
Platelet Count	x10 ⁹ /L		100	550
White Blood Cell Count (WBC)	x10 ⁹ /L		3	20

Clinical Chemistry				
Laboratory Parameter	Units	Category	Clinical Concern Range	
			Low Flag (< x)	High Flag (>x)
Albumin	G/L		30	
Calcium	mmol/L		2	2.75
Creatinine	umol/L			1.3 X ULN
Creatinine	umol/L	Δ from BL		↑ 44.2
Glucose	mmol/L		3	9
Potassium	mmol/L		3	5.5
Sodium	mmol/L		130	150
Total CO ₂	mmol/L		18	32

11.6. Appendix 6: Multicentre Studies

A summary table for subject disposition will be displayed by centre, no other outputs will be produced by centre or highlighting the recruitment by site.

11.7. Appendix 7: Examination of Covariates, Subgroups & Other Strata

All the reporting will be separated by subject group, i.e. by healthy volunteers and pSS subjects. Subject group would be fitted as a fixed categorical variable in the ANOVA model described in Section [7.1.1.4](#).

11.8. Appendix 8: Multiple Comparisons & Multiplicity

No adjustments for multiplicity will be required.

11.9. Appendix 9: Model Checking and Diagnostics for Statistical Analyses

11.9.1. Statistical Analysis Assumptions

Endpoint(s)	
 • ¹¹C-MET PET/CT parameters including but not limited to SUV_{peak}, SUV_{max} and SUV_{mean}. • Multiparametric MRI parameters including but not limited to diffusivity (D), microvascular volume fraction (f) and K_{trans}. • Additional quantitative parameters, if deemed appropriate.
Analysis	
 • Analysis of Variance (ANOVA) • Distributional assumptions underlying the model used for analysis will be examined by obtaining a normal probability plot of the residuals and a plot of the residuals versus the fitted values (i.e. checking the normality assumption and constant variance assumption of the model respectively) to gain confidence that the model assumptions are reasonable. • If there are any departures from the distributional assumptions, alternative models will be explored using appropriate transformed data. Mann-Whitney U test will also be used when untransformed data cannot be assumed to be normal.
Endpoint(s)	
 • Correlation between imaging parameters with 
 ○ other imaging parameters ○ salivary and tear flow ○ histological scores ○ disease activity ○ lab biomarkers of disease activity
Analysis	
 • Pearson Correlation Coefficient • Both variables should be normally distributed • Linear relationship between each of the two variables • Homoscedasticity of the data – equally distributed about the regression line. • Alternative, non-parametric method such as Spearman rank correlation will also be reported if assumptions are violated.

11.10. Appendix 10 – Abbreviations & Trade Marks

11.10.1. Abbreviations

Abbreviation	Description
ADC	Apparent Diffusion Coefficient
AE	Adverse Event
ANOVA	Analysis of Variance
Anti-SSA/B	Anti-Sjögren's-syndrome-related antigen A/B
A&R	Analysis and Reporting
CI	Confidence Interval
CSR	Clinical Study Report
CT	Computed Tomography
CV _b / CV _w	Coefficient of Variation (Between) / Coefficient of Variation (Within)
D	Pure Diffusion Coefficient
D*	Pseudo Diffusion Coefficient
DOB	Date of Birth
DCE	Dynamic Contrast Enhanced
DP	Decimal Places
DW	Diffusion Weighted
ECG	Electrocardiogram
eCRF	Electronic Case Record Form
ESSDAI	EULAR Sjögren's Syndrome Disease Activity Index
ESSPRI	EULAR Sjögren's Syndrome Patient Reported Index
EULAR	European League Against Rheumatism
f	Micro vascular volume fraction
FDG	Fluorodeoxyglucose
FRP	Females of Reproductive Potential
FSH	Follicle Stimulating Hormone
HV	Healthy Volunteers
IA	Interim Analysis
ICH	International Conference on Harmonisation
IDSL	Integrated Data Standards Library
IHC	Immune Histochemistry
IP	Investigational Product
IRE	Initial Rate of Enhancement
IV	Intravenous
K _{trans}	Exchange Rate
ME	Maximal Enhancement
MET	Methionine
MRI	Magnetic Resonance Imaging
mSv	Millisievert
NRS	Numeric Rating Scale
PCI	Potential Clinical Importance
PD	Pharmacodynamic

Abbreviation	Description
PDMP	Protocol Deviation Management Plan
PET	Positron Emission Tomography
PK	Pharmacokinetic
pSS	Primary Sjögren's Syndrome
QC	Quality Control
QTcF	Frederica's QT Interval Corrected for Heart Rate
QTcB	Bazett's QT Interval Corrected for Heart Rate
RAP	Reporting & Analysis Plan
ROI	Region of Interest
SAC	Statistical Analysis Complete
SAE	Serious Adverse Event
SD	Standard Deviation
SOP	Standard Operation Procedure
SUV	Standardised uptake value
TFL	Tables, Figures & Listings
TIV	Total Inflammatory Volume
GSK	GlaxoSmithKline

11.10.2. Trademarks

Trademarks of the GlaxoSmithKline Group of Companies
HARP

Trademarks not owned by the GlaxoSmithKline Group of Companies
SAS

11.11. Appendix 11: List of Data Displays

11.11.1. Data Display Numbering

The following numbering will be applied for RAP generated displays:

Section	Tables	Figures
Study Population	1.1 to 1.6	NA
Pharmacodynamic	2.1 to 2.9	2.1 to 2.13
Pharmacokinetic	3.1 to 3.3	3.1 to 3.2
Safety	4.1 to 4.5	NA
Biomarker	5.1 to 5.11	5.1 to 5.9
Section	Listings	
ICH Listings	1 to 21	
Other Listings	22 to 47	

11.11.2. Mock Example Shell Referencing

Non IDSL specifications will be referenced as indicated and if required an example mock-up displays provided in [Appendix 12: Example Mock Shells for Data Displays](#).

Section	Figure	Table	Listing
Study Population	NA	POP_Tn	POP_Ln
Pharmacodynamic	EFF_Fn	EFF_Tn	EFF_Ln
Pharmacokinetic	PK_Fn	PK_Tn	PK_Ln
Biomarker	PD_Fn	PD_Tn	PD_Ln

NOTES:

- Non-Standard displays are indicated in the 'IDSL / TST ID / Example Shell' or 'Programming Notes' column as '[Non-Standard] + Reference.'

11.11.3. Deliverable [Priority]

Delivery [Priority] ^[1]	Description
SAC	Final Statistical Analysis Complete

NOTES:

- Indicates priority (i.e. order) in which displays will be generated for the reporting effort.

11.11.4. Study Population Tables

Study Population Tables					
No.	Population	IDSL / TST ID / Example Shell	Title	Programming Notes	Deliverable [Priority]
Disposition					
1.1.	Safety	ES1	Summary of Subject Disposition		SAC
1.2.	Safety	NS1	Summary of Number of Subjects by Centre ID		SAC
Populations Analysed					
1.3.	Screened	SP1	Summary of Study Populations		SAC
Demography					
1.4.	Safety	DM1	Summary of Demographic Characteristics for all Enrolled Subjects	Include summary of disease duration for pSS patients.	SAC
1.5.	Safety	DM1	Summary of Demographic Characteristics for Subjects Undergone a Scan	Include summary of disease duration for pSS patients. Exclude subjects who have not completed at least one scan.	SAC
1.6.	Safety	DM6	Summary of Race and Racial Combination		SAC
Concomitant Medications and Medical Conditions					
1.7.	Safety	CM1	Summary of Concomitant Medications		SAC

11.11.5. Pharmacodynamic Tables

Pharmacodynamic: Tables					
No.	Population	IDSL / TST ID / Example Shell	Title	Programming Notes	Deliverable [Priority]
¹⁸F-FDG PET/CT semi-quantitative parameters					
2.1.	Safety	EFF_T1	Summary of ¹⁸ F-FDG PET/CT parameters	Paginate by Parameter. Subheading 'Parameter: [name]'	SAC
¹¹C-MET PET/CT semi-quantitative parameters					
2.2.	Safety	EFF_T1	Summary of ¹¹ C-MET PET/CT parameters	Paginate by Subject group and Parameters. To include ROI, side and SE with all other summary statistics. Subheading: 'Parameter: [name]' 'Subject Group: [name]'	SAC
2.3.	Safety	EFF_T4	Point Estimate and 95% CI for ¹¹ C-MET PET/CT Derived Parameters of Difference in pSS vs. HV	Analysed by Parameter (SUVmean/SUVmax/SUVpeak) and ROI. When applicable for a given ROI, the analysis will be separated by the side. Summarize Means and Differences (or Ratios) with 95% CI.	SAC

Pharmacodynamic: Tables					
No.	Population	IDSL / TST ID / Example Shell	Title	Programming Notes	Deliverable [Priority]
2.4.	Safety	EFF_T5	Summary of the Posterior Distribution of the Ratio and Difference of Group Means for ¹¹ C-MET PET/CT Parameter by Region	Paginate by parameter and subject group. Parameters to include: SUVpeak, SUVmax and SUVmean. First two columns for ROI and side.	SAC
2.5.	Safety	EFF_T6	Posterior Probability that the Ratio and Difference of Group Means for ¹¹ C-MET PET/CT Parameter Exceeds a Certain Value, by Region	Paginate by parameter and subject group. Parameters to include: SUVpeak, SUVmax and SUVmean. First two columns for ROI and side. Ratios of interest: 1, 1.5 and 2 Difference of interest: 0 Footnote: Ratio=HV/pSS Note: Values/inequality subject to change based on data	SAC

Pharmacodynamic: Tables					
No.	Population	IDSL / TST ID / Example Shell	Title	Programming Notes	Deliverable [Priority]
Multiparametric MRI quantitative parameters					
2.6.	Safety	EFF_T1	Summary of Multiparametric MRI.	
Paginate by Subject group and Parameters include (median and IQR) Ktrans, D, D*, f, ADC, IRE, ME, and (Mean) lipid content and gland volume as data permits.
 
To include ROI, side (low/high/aggregated), and SE with all other summary statistics.
 
Parameters to include:
	SAC
2.7.	Safety	EFF_T4	Point estimate and 95% CI for Multiparametric MRI Derived Parameter of Difference in pSS vs. HV	
Analysed by Parameter and Region of Interest.
 
When applicable for a given ROI, the analysis will be separated by the side of the ROI.
 
Parameters include (median and IQR) Ktrans, D, D*, f, ADC, IRE, ME, and (Mean) lipid content and gland volume as data permits.
 
Summarize Means and Differences (or Ratios) with 95% CI.
 
Note: P value not included as this is not a statistically powered study
	SAC

Pharmacodynamic: Tables					
No.	Population	IDSL / TST ID / Example Shell	Title	Programming Notes	Deliverable [Priority]
2.8.	Safety	EFF_T5	Summary of the Posterior Distribution of the Ratio and Difference of Group Means for Multiparametric MRI Parameter by Region	Paginate by parameter and subject group. Parameters to include but not limited to: Ktrans, ADC, D, and f. For each median values will be analysed. First two columns for ROI and side.	SAC
2.9.	Safety	EFF_T6	Posterior Probability that the Ratio and Difference of Group Means for Multiparametric MRI Parameter Exceeds a Certain Value, by Region	Paginate by parameter and subject group. Parameters to include but not limited to: Ktrans, ADC, D, f and volume. For each median values will be analysed. First two columns for ROI and side. Ratios of interest: 1, 1.5 and 2 Difference of interest: 0 Footnote: Ratio=HV/pSS Note: Values/inequality subject to change based on data	SAC

Note: The above summaries will be generated if data is available.

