Planned Analyses	
 • Interim analyses are detailed within Section 3.1 where applicable. • All decisions regarding final analysis, as defined in this RAP document, will be made prior to Database Freeze of the study data.
Analysis Populations	
 • The Screened Population (Comprises of subjects who sign the Informed Consent) will be used for the evaluation of Screen Failure subjects • The Safety Population (Comprised of all subjects who receive/undergo any Visit 1 procedure). will be used for the evaluation of Study Population and Safety. • The Pharmacokinetic (PK) Population (Comprised of subjects in the ‘Safety’ population for whom radio-pharmacokinetic sample was obtained and analysed) will be used for the evaluation of Pharmacokinetic Analysis.
Hypothesis	
 • There are no formal hypotheses being tested in the study; instead an estimation and inference approach will be adopted to evaluate the objectives.
Primary Analyses	
 • Descriptive statistics and graphical displays, if appropriate, will be presented for all FDG PET/CT derived parameters across the regions of interest (ROI) for all pSS subjects and for all ¹¹C-MET PET/CT and MRI derived parameters across the ROI for all healthy volunteers and pSS subjects. • An exploratory comparison of pSS subjects vs healthy volunteers may be performed for each ¹¹C-MET PET/CT and MRI derived quantitative parameter as data permit, to estimate a difference (or ratio if log transformation is needed) with 95% confidence interval.
Secondary Analyses	
 • Descriptive statistics and graphical displays, if appropriate, will also be presented for all derived parameters from dynamic PET imaging and PK analyses. • If data permits, statistical analyses of ¹¹C-MET PET radio-PK modelling indices with ¹¹C-MET static imaging matrices will be conducted to assess correlation.

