7.1.3. Bayesian Analysis

In addition, a Bayesian approach to the exploratory comparison of pSS vs HV analysis of the ¹¹C-MET PET/CT and multi-parametric MRI parameters will be used. The objective of this analysis is to allow interpretable probability statements for the difference in two groups.

For the endpoints defined in Section [7.1.2](#), the uncertainty of the endpoint will be described with probability density function p(μ), say, where ‘μ’ represents the parameter. P(μ) represents our ‘prior belief’, since very little is known about the distribution of such parameters, normal function is assumed to be suitable for the data. This will have an unknown mean and known variance taken from the raw data (i.e x_j~N(μ_j,σ_j²) where j is

the pSS patient group or the HV group). A weakly-informative (vague) conjugate Normal prior density function with mean zero and a large variance will be adopted for the group mean ($P(\mu)=N(0,100^2)$).

The endpoint from the study data will be used to gather evidence, which will be characterised via its likelihood function (derived from the relevant sampling distribution, $l(x|\mu)$, say, where 'x' stands for 'data' or in our case the parameter values).

This will lead to a Normal posterior density function for the endpoints of interest. Should the data not support a Normal likelihood function, alternative parametric forms, such as a log-Normal density, will be investigated.

Bayes' theorem will be applied to derive the posterior density function $p(\mu_j, x_j)$. PROC MCMC will be used for the analysis in SAS. The number of burn-in iterations will be at least 10,000 and the number of MCMC iterations, excluding the burn-in iterations will be at least 5000.

The posterior distribution for each endpoint will be summarised by region and group, including mean, median, SD, interquartile range and 95% credible interval based on highest posterior density (HPD) interval.

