Samples from the posterior distribution for the group mean $p(\mu_j, x_j)$ for the pSS patients and for the HV subjects will be used to determine the posterior distribution for the ratio and difference of group means (pSS patients to the HV subjects). The posterior distribution for the ratio and difference of group means will be summarised by region and endpoint. Plots for the mean and 95% credible interval for the posterior distribution of the group mean and the difference of group means will be presented for each endpoint and region. Samples from the posterior distribution of the ratio of group means will be used to determine the probability that the ratio of the endpoints in pSS patients to HV subjects exceed 1 for each endpoint and region. This will be repeated for other values to allow us to plot a graph of probability of exceeding a certain value, for ratios of 1, 1.5 and 2. The ratio will be given such that group expected to have lower uptake will be used at the reference (denominator).

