Mean SUV	Parotid Gland	pSS (N=xx)	normal(0, sd = 100)	1	x.xx	x.xx	x.xx	x.xx	x.xx	(x.xx,x.xx)
		HV (N=xx)	normal(0, sd = 100)	1	x.xx	x.xx	x.xx	x.xx	x.xx	(x.xx,x.xx)
		Difference			x.xx	x.xx	x.xx	x.xx	x.xx	(x.xx,x.xx)
		Ratio			x.xx	x.xx	x.xx	x.xx	x.xx	(x.xx,x.xx)
	Submandibular Gland									

pSS=primary Sjogren's Syndrome patients HV=Health Volunteers, ROI = Region of Interest

CONFIDENTIAL

203818

Number of MCMC iterations, excluding the burn-in iterations = 5,000. Number of burn-in iterations = 10,000
The PET parameters are assumed to follow a normal distribution with unknown mean Θ and known variance σ^2 (i.e. $N(\Theta, \sigma^2)$).
Difference calculated as pSS-HV and ratio as pSS/HV. 95% credible intervals based on the highest posterior density interval.

Example: EFF_T6
Protocol: 203818
Population: Safety

Page 1 of n

Posterior Probability that the Ratio and Difference of Group Means for [Imaging Method] Parameter Exceeds a Certain Value, by Region

Parameter (units)	Region	P(ratio) > 0.5	P(ratio) > 1	P(ratio) > 1.5	P(Difference) > 0
Mean SUV					

Note: P(ratio) > 1 is the probability that the posterior ratio of group means exceeds 1 based on 5,000 simulated posterior predicted values. *Ratio of pSS patients to Healthy Volunteers and difference of pSS-HV.*

Example : EFF_T7
 Protocol : 203818
 Population : Safety

Page 1 of n

Table X.X
 Summary of ESSDAI Component Scores
 Activity Level

Domain	No	Low	Moderate	High
Constitutional	n(%)	n(%)	n(%)	NA
Lymphadenopathy	n(%)	n(%)	n(%)	n(%)
Glandular	n(%)	n(%)	n(%)	NA
Articular	n(%)	n(%)	n(%)	n(%)
Cutaneous	n(%)	n(%)	n(%)	n(%)
Pulmonary	n(%)	n(%)	n(%)	n(%)

CONFIDENTIAL

203818

Renal	n(%)	n(%)	n(%)	n(%)
Muscular	n(%)	n(%)	n(%)	n(%)
PNS	n(%)	n(%)	n(%)	n(%)
CNS	n(%)	NA	n(%)	n(%)
Haematological	n(%)	n(%)	n(%)	n(%)
Biological	n(%)	n(%)	n(%)	NA

Example : EFF_L1
Protocol : 203818
Population : Safety

Listing xx
Listing of ¹⁸F-FDG PET/CT Parameters

Imaging Parameter

Subject	ROI	SUV _{mean}	SUV _{peak}	SUV _{max}	TR	TIV
xxxxx	Parotid Left					
	Parotid Right					
					

SUV= Standardised Uptake Value, TR = tissue-to-reference ratio ,TIV = total inflammatory volume.(description of all Parameter)

Example : EFF_L2
Protocol : 203818
Population : Safety

Page 1 of n

Listing No. XX

Listing of Tracer and Contrast Agent Administration Volume

Subjid	Visit	Contrast Agent/Tracer	Volume of Administration (Unit)
xxx	Visit1	Gadolinium	x
	Visit1	C-MET	x
	Visit2	FDG	x

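### Tables 2.5 and 2.9 let the cut-offs and inequality direction of the posterior probabilities change with the data; if direction follows the observed sign, the null rate of displayed values above 0.95 doubles

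*SAP*

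**What the plan says.** SAP 7.1.3 uses posterior samples to "determine the probability that the ratio of the endpoints in pSS patients to HV subjects exceed 1 for each endpoint and region", and repeats this for ratios of 1.5 and 2. It then gives a direction rule: "The ratio will be given such that group expected to have lower uptake will be used at the reference (denominator". It does not name the group expected to be lower for any endpoint.

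The programming notes to Table 2.5 (MET PET) and Table 2.9 (MRI) in SAP 11.11.5 read "Ratios of interest: 1, 1.5 and 2 Difference of interest: 0 Footnote: Ratio=HV/pSS", and both end with "Note: Values/inequality subject to change based on data". Shell EFF_T6 in SAP 11.12, which serves both tables, states "Ratio of pSS patients to Healthy Volunteers and difference of pSS-HV" and has ratio columns for 0.5, 1 and 1.5.

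On timing, the SAP synopsis says "All decisions regarding final analysis, as defined in this RAP document, will be made prior to Database Freeze of the study data".

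On the model, 7.1.3 says of the normal likelihood "This will have an unknown mean and known variance taken from the raw data", and of the prior "A weakly-informative (vague) conjugate Normal prior density function with mean zero and a large variance will be adopted for the group mean". The prior SD is 100.

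**The concern.** A one-directional tail probability measures evidence for a claim in the usual calibrated sense only if the claim was chosen independently of the result. Here the claim consists of a direction and a cut-off, and the note allows both to be chosen after the result is known. It replaces the expectation rule of 7.1.3 with observation. It also sits badly with 7.1.3's stated purpose, which is to give probability statements about the group difference that can be interpreted.

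Reconciling the conflicting ratio directions would not be enough on its own, because the note would still allow the agreed direction to be turned afterwards. A reader of the final table could not tell whether a direction had been set in advance or picked.

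**Working it through.** **Inputs.** Healthy volunteers (HV) 4 to 12, at most 8 with MET PET; pSS 8 to 12 (SAP synopsis, protocol 4.3). MET SUVmax in healthy volunteers: mean 6.00, SD 1.5 (protocol 9.2). No pSS SD is given for MET, so I assume the same value. Ktrans: 0.20 (SD 0.04) in healthy volunteers and 0.26 (SD 0.05) in pSS (protocol 9.2).

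**The plan's own figure.** The only sample-size figure is the precision table in protocol 9.2. t(0.975, n-1) x SD/sqrt(n) with SD 1 gives 1.591, 0.836 and 0.635 for n = 4, 8 and 12, matching the printed 1.59, 0.84 and 0.64. The documents state no operating characteristic for Tables 2.5 or 2.9.

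**Formula.** The prior is negligible: the sampling variance of a mean is at most about 1.5^2/4 = 0.56, against a prior variance of 10,000. So

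P = Phi[(mean pSS - mean HV) / sqrt(s^2_pSS/n_pSS + s^2_HV/n_HV)].

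With means well above zero, P(ratio > 1) is practically P(difference > 0). If the direction follows the observed sign, the table shows max(P, 1-P).

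**No true difference, variance known.** P is uniform on 0 to 1.
- Fixed direction: Pr(P > 0.95) = 5%, median 0.50.
- Direction by sign: Pr(P > 0.95) + Pr(P < 0.05) = 10%. The displayed value is uniform on 0.5 to 1, so its median is 0.75.

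**No true difference, SAP model.** 1,000,000 simulated trials per setting, sample variances treated as known. Share of trials with a displayed probability above 0.95:

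| HV / pSS | MET SDs, fixed | MET SDs, by sign | Ktrans SDs, fixed | Ktrans SDs, by sign |
|---|---|---|---|---|
| 4 / 8 | 7.3% | 14.6% | 6.9% | 13.9% |
| 4 / 12 | 7.6% | 15.2% | 7.1% | 14.2% |
| 8 / 8 | 6.1% | 12.2% | 6.2% | 12.4% |
| 8 / 12 | 6.0% | 12.0% | 5.9% | 11.8% |
| 12 / 8 (MRI only) | 6.0% | 12.0% | 6.2% | 12.3% |
| 12 / 12 (MRI only) | 5.7% | 11.5% | 5.7% | 11.5% |

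By-sign is twice fixed in every row, within simulation error and rounding. The median displayed value by sign is 0.75 to 0.76.

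**One direction chosen for a whole table.** Illustration with 9 rows, HV 8 and pSS 12, and an assumed between-row correlation of 0 to 0.95. From 39% down to 7% of rows then point against the displayed direction, and 9.2% to 12.0% of rows exceed 0.95.

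**Do the listed cut-offs suit Ktrans?** The protocol's ratio is 0.26/0.20 = 1.3. With 12 per group and variances taken as known, let z_c = (0.26 - 0.20c)/sqrt[(0.05^2 + c^2 x 0.04^2)/12]. Averaged over data sets, P(pSS/HV > c) is Phi(z_c/sqrt 2).
- c = 1: z = 0.06/0.0185 = 3.25; average 0.99
- c = 1.2: z = 0.02/0.0200 = 1.00; average 0.76
- c = 1.5: z = -0.04/0.0226 = -1.77; average 0.10
- c = 2: z = -0.14/0.0272 = -5.14; average 0.00

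In the printed HV/pSS direction:
- c = 1: 1 - 0.99 = 0.01
- c = 1.5: z = (0.20 - 0.39)/0.0245 = -7.7; average 0
- c = 2: z = (0.20 - 0.52)/0.0311 = -10.3; average 0

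Healthy volunteers are the lower group in these figures, so the rule in 7.1.3 would give pSS/HV for Ktrans, whereas the Table 2.9 footnote gives HV/pSS.

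**The case against.** The case for leaving the note alone has several parts.

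- **Exploratory study.** No hypothesis is tested, no p-values are presented and no posterior threshold is set. SAP 7.1.2 rests interpretation on point estimates and 95% intervals. This stands: 0.95 is an illustrative benchmark, and no stated error rate is breached.
- **The information is not lost.** At ratio 1 or difference 0, the opposite probability is one minus the one shown. Tables 2.3 and 2.7 give the contrast with intervals, and the shell behind Tables 2.4 and 2.8 fixes pSS-HV and pSS/HV, so the sign stays visible. This stands for ratio 1 and difference 0. It does not help at other cut-offs: P(HV/pSS > 1.5) near 0 says nothing about P(pSS/HV > 1.5).
- **A low probability at 1.5 is itself informative.** This is true, because it says so large a ratio is unlikely. But a grid that jumps from 1 to 1.5 cannot describe an effect of 1.3.

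Four stronger readings are tempting, and the documents do not support them.

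- A reader might infer that the table would always favour the displayed direction. The note permits a change but does not require one for each row, and EFF_T6 has one set of column headings. With one direction per table, some rows point the other way.
- A reader might infer that choosing the direction more than doubles the rate. It exactly doubles it. The excess over 10% comes from treating sample variances as known, which also lifts the fixed-direction rate above 5% and would survive this fix.
- A reader might infer a certain breach of the database-freeze rule. The note gives no timing, so a change could be made before freeze. That would not make it independent of the data, since the study is open label (protocol 6.2) and imaging parameters are reviewed during it (SAP 3.1).
- A reader might infer that a turned probability is false. It is still the model's posterior probability of the printed statement. What is lost is calibration, because the statement was selected.

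**Conclusion.** The point holds as a matter of selection. The SAP gives open-ended permission to choose direction and cut-offs from the data, and no other text fixes either. If the direction follows the observed sign row by row, the null rate of a displayed probability above 0.95 doubles: 5% to 10% with known variance, and 5.7-7.6% to 11.5-15.2% under the SAP's model across the planned sample sizes. The median displayed value at ratio 1 moves from 0.50 to about 0.75.

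These figures assume normal data, equal SDs for MET and the protocol's SDs for Ktrans. The effect of data-driven cut-offs was not quantified. The Ktrans example shows that the printed values may not suit the protocol's own figures, so there would be a reason to change them.

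This does not invalidate the comparison of groups, because the interval estimates are unaffected by the direction chosen. It is an improvement worth making because it costs almost nothing.

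**What to change.** 1. Delete the note from Tables 2.5 and 2.9.
2. In SAP 7.1.3, name one ratio direction for each endpoint and one fixed cut-off grid that includes values between 1 and 1.5. Do this before imaging results are compared by group. A limit at database freeze alone would not be early enough.
3. Bring the two statements in 7.1.3, the footnotes and cut-offs of Tables 2.5 and 2.9, and shell EFF_T6 into line with that choice.
4. Label any later change of direction or cut-off as post hoc in the table itself.

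The cost is SAP wording and a few extra columns from the same posterior draws. No additional data are needed. The plug-in variance needs its own correction and is not addressed here.
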